8.1.3 Benefits

When evaluating the risks and benefits of the proposed study, it is believed that risks are relatively minimal when compared to the potential [REDACTED] benefits that subjects are likely to receive. The benefits of receiving Woebot include potentially improving mood (anxiety, stress, and/or depression), acquiring practical psychotherapeutic skills (from cognitive behavioral therapy, dialectical behavior therapy, and mindfulness), and receiving psychoeducation about mental health.

Participants who improve mood may derive additional benefits should said mood improvements be associated with other psychological improvements such as interpersonal or occupational functioning. Study of the effectiveness of this intervention will also benefit society more generally by providing data on the utility of Woebot t.

8.2 Adverse Events

8.2.1 Definitions

Adverse Event (AE): An AE is any unanticipated medical occurrence in a clinical study participant using an investigational product or from study procedures that does not necessarily have a causal relationship with this product. An AE can therefore be any unfavorable and unintended sign (including an abnormal laboratory finding), symptom, or disease temporally associated with the use of an investigational product, whether or not related to the investigational product.

Serious Adverse Event (SAE): Any SAE is any AE that meets any of the following criteria:

- Results in *death*
- Is *life-threatening*
- Requires inpatient *hospitalization* or prolongation of existing hospitalization
- Results in persistent or significant *disability/incapacity*
- Is a *congenital anomaly/birth defect*
- Is an *important medical event* that may not result in death, be life-threatening, or require hospitalization may be considered a serious adverse event when, based upon appropriate medical judgment, they may jeopardize the patient or subject and may require medical or surgical intervention to prevent one of the outcomes listed above.

Unanticipated Problem (UAP): A UAP is an incident, experience, or outcome that meets all of the following criteria:

- Unexpected in nature, severity, or frequency (i.e., not described in study-related documents such as the IRB- or IEC-approved protocol or consent form)
- Related or possibly related to participation in the research (i.e., possibly related means there is a reasonable possibility that the incident experience or outcome may have been caused by the procedures involved in the research)
- Suggests that the research places subjects or others at greater risk of harm (including physical, psychological, economic, or social harm).

An individual AE observed during the conduct of a study may be considered an unanticipated study problem involving risk to human subjects, and reported to the IRB, only if it is unexpected, serious, and would have implications for the conduct of the study (e.g., requiring a significant and, usually, safety-related change in the protocol such as revising the inclusion/exclusion criteria or including a new monitoring requirement or informed consent). Investigators should report possible UAP to the Sponsor and the Sponsor will make a determination for the UAP in the context of the study and any change to the study.

Adverse Device Effect (ADE): Any adverse event related to the use of an investigational medical device. This includes any adverse event resulting from insufficiencies or inadequacies in the instructions for use, the deployment, the implantation, the installation, the operation, or any malfunction of the investigational medical device. This also includes any event that is a result of a use error or intentional misuse.

Unanticipated Adverse Device Effect (UADE): Any serious adverse effect on the health or safety, or any life-threatening problem or death caused by or associated with a device which was not previously identified in nature, severity or degree of incidence in the protocol, Instructions for Use, Summary of Previous Studies Document, or other sources of information for the investigational product. Additionally, a UADE is any other unanticipated serious problem associated with the investigational device that relates to the rights, safety, or welfare of subjects.

UADEs will include events meeting either A or B as stated below:

A. Events meeting ALL of the following criteria:

- Not included in the list of Anticipated Events (refer to protocol section 8.2.2)
- Related (possibly, probably, or definitely) to the investigational device per the site principal investigator
- Serious (meets any of the SAE criteria)

B. Any other unanticipated serious problem associated with the investigational device that relates to the rights, safety, or welfare of participants.

Device Deficiencies: Inadequacy of a medical device related to its identity, quality, durability, reliability, safety or performance, such as malfunction, misuse or use error and inadequate labeling. The reporting of a Device Deficiency is a Product Complaint.

Product Complaints: Any written, electronic, or oral communication that alleges deficiencies related to the identity, quality, durability, reliability, safety, effectiveness, or performance of a device after it is released for distribution.

8.2.2 Previously Noted Adverse Device Effects

Any ADE that is not identified in nature, severity, or is not listed below is considered unanticipated:

- There are no known ADEs at the time of writing this protocol.

8.3 Assessment of Adverse Events

Due to the low-risk profile of this study, adverse and serious adverse events are not anticipated. The investigator will be alert to any complaints or adverse reactions that arise and will take appropriate steps to alleviate the difficulties as soon as possible.

Existing disclaimers that the ‘Build’ app is not intended for crisis management will be presented in the ICF and at onboarding. Adverse events (AEs) will be assessed via:

- 1) Spontaneous participant self reports communicated outside of the ‘Build’ app
- 2) Direct participant self reports collected via the Week 2 survey at EOS
- 3) Language Detection Protocol (e.g., helplines feature)
- 4) Upon review of select conversations/transcripts with Woebot

All potential AE/SAE triggers described above will follow a predetermined safety protocol as outlined in a Safety Management Plan (SMP). In the event of a suspected AE, the Principal Investigator would be immediately alerted, and unblinded if indicated, as well as provided with all available clinical and other details of the event. Based on the initial report, appropriate steps would be taken to gather further information from the participant as needed, address the AE/SAE, and complete reporting requirements. The study team will make every effort to follow-up with the participant within 3 business days of the initial report.

8.3.1 Time Frame

Collection of AEs and SAEs will begin at ICF signature, and will continue through End of Study (EOS) at Week 2.

8.3.2 AE Severity

Investigators will grade the severity of all AEs using the Common Terminology Criteria for Adverse Events (CTCAE). If possible, investigators should report event terms that reflect a single, unifying diagnosis rather than individual signs or symptoms (e.g., “influenza” instead of “coughing, body aches, fever;” and “anemia” rather than “low hemoglobin”).

If an AE term is not listed in the CTCAE criteria, a corresponding grading is to be performed by the investigator based on his/her best medical judgment as follows:

- **Mild (Grade 1):** asymptomatic or mild symptoms; clinical or diagnostic observations only; intervention not indicated
- **Moderate (Grade 2):** minimal, local, or noninvasive intervention indicated; limited age-appropriate instrumental activities of daily living (ADL)
- **Severe (Grade 3):** medically significant but not immediately life-threatening; hospitalization or prolongation of hospitalization indicated; disabling; or limiting self-care ADL
- **Life-threatening (Grade 4):** life-threatening consequences; urgent intervention indicated
- **Fatal (Grade 5):** death related to an AE

8.3.3 AE Causality

An event's relatedness to the investigational device will be determined by the Principal Investigator and classified under the following causality ratings:

- **Non-related:** There is no evidence of any causal relationship.
- **Related:** There is clear evidence of a causal relationship between the device and event; all other explanations have been ruled out.

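### The two-level causality scale in section 8.3.3 cannot supply the relatedness levels that the UADE definition in section 8.2.1 counts, so serious events with inconclusive evidence have no defined classification

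*Combined protocol and SAP*

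**What the plan says.** Section 8.3.3 has the Principal Investigator rate each event's relatedness to the device on a two-level scale.

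- The lower rating, *Non-related*, applies on this condition: "There is no evidence of any causal relationship".
- The upper rating, *Related*, sets a far stricter condition: "There is clear evidence of a causal relationship between the device and event; all other explanations have been ruled out".

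Section 8.2.1 says that an event is a UADE if it meets limb A or limb B.

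- Limb A has three criteria, all of which must be met: the event is not on the anticipated list, it is serious, and it satisfies "Related (possibly, probably, or definitely) to the investigational device per the site principal investigator".
- Limb B is a residual category: "Any other unanticipated serious problem associated with the investigational device that relates to the rights, safety, or welfare of participants".
- The general sentence before the limbs is also broad, covering "any life-threatening problem or death caused by or associated with a device".

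The anticipated list that limb A refers to is in section 8.2.2, and it is empty: "There are no known ADEs at the time of writing this protocol".

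Section 10.4.1 makes the frequency of AEs, SAEs and UADEs an exploratory safety measure. Section 10.4.2 gives device relatedness as an example of what will be described, and asks for n (%) for each safety endpoint.

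**The concern.** The two ratings in section 8.3.3 sit at the extremes. One needs no evidence at all; the other needs clear evidence and the exclusion of every alternative. Limb A is written for a graded scale that includes the ground between them. The protocol therefore asks the investigator for a judgement in one section that the scale in another section cannot record.

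The gap lies where difficult cases are likely to arise. The study enrols adults with or without clinical symptoms and records psychiatric history and concurrent medication or therapy (sections 6.1.2 and 6.1.3). The Week 2 survey asks about changes in health, new suicidal thoughts and symptom-driven changes in care, and feeds the UADE determination (section 8.5.3). For such events an existing condition or another treatment is an obvious competing explanation, so excluding all alternatives would often be hard. That is an inference; the protocol gives no rate.

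At stake are the UADE count and the device-relatedness summary. The gap in section 8.3.3 applies to every event it rates, so the relatedness summary could also be affected by non-serious events. AE and SAE frequencies do not depend on the rating, and neither do the CSQ-8 analyses.

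**Working it through.** The protocol gives no figure to reproduce here. The check sets the two sections side by side and then looks for a rule that connects them.

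**Step 1. Map the state of evidence to each section.**

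| Evidence of a causal link | Rating under 8.3.3 as worded | Relatedness criterion in limb A (8.2.1) | Agreement |
|---|---|---|---|
| None | Non-related | Not met | Consistent |
| Some, alternatives remain (possible) | Neither definition met | Met | Undefined |
| Stronger, alternatives remain (probable) | Neither definition met | Met | Undefined |
| Clear, alternatives excluded (definite) | Related | Met | Consistent |

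Of the three levels that limb A counts, one has a matching rating in section 8.3.3 and two do not.

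**Step 2. See how much of limb A rests on relatedness.** Take any SAE.

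- Not on the anticipated list: always met, because section 8.2.2 lists zero effects.
- Serious: met, because the event is an SAE.
- Related: the only criterion left to decide.

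If *Related* is applied as worded, possibly and probably related SAEs fall outside limb A. If limb A is applied as worded, they count. The two readings give opposite answers for the same event.

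**Step 3. Look for a mapping rule.**

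- Section 8.4 requires the relationship to be assessed and an AE/SAE form completed, but gives no levels.
- Section 8.6 refers to confirming the assessment of causality in the context of the Safety Assessment Committee, also without a scale.
- The unanticipated-problem definition in section 8.2.1 has an intermediate level, under which "possibly related means there is a reasonable possibility that the incident experience or outcome may have been caused". That definition concerns research procedures, not the device. It shows that the protocol uses such a threshold elsewhere, but it does not fill the gap.

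No rule was found.

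**Step 4. Scale.** The protocol gives no event rate and no split by relatedness level, so no expected count can be calculated. The weight of one reclassified participant can be shown. The visible text defines no safety denominator. I assume the roughly 165 randomized participants (section 5), allocated 1:1 (section 3.3.2), and tabulation by arm for the second figure.

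- Overall: 1/165 = 0.61%.
- Per arm: 165/2 = 82.5, so 1/82 = 1.22% or 1/83 = 1.20%.

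These figures show what one participant weighs. They do not estimate the error.

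**The case against.** The strongest reply is that little follows from the mismatch.

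- **Limb B and the opening UADE sentence** require only association with the device and do not depend on the section 8.3.3 rating. With no effects listed as anticipated, a possibly related SAE could enter there. This stands as a limit: total UADEs fall only if limb B is also read narrowly. But association is not defined, and limb B repairs neither limb A nor the relatedness summary.
- **Other documents** may hold a working rule. Section 8.3 says events follow a Safety Management Plan, and section 8.4 refers to an assessment form. Neither was available. Even if one of them has a finer scale, the protocol's own two sections would still disagree.
- **Committee review** under section 8.6 may mean that the investigator's rating is not the last step. With no scale stated there, this does not settle how an inconclusive event is classed.
- **The main safety actions do not use the rating.** Discontinuation depends on SAE grade (section 5.3), the study hold on the number or severity of AEs (section 7), and follow-up on a suspected AE (section 8.3). This is correct. The effect shown here is on descriptive safety reporting.
- **One site and one Principal Investigator** make disagreement between raters unlikely. This also stands. The remaining risk is that the same rater resolves the gap differently from event to event.
- **There may be no such events.** This is conceded: section 8.3 does not expect adverse events in this low-risk, two-week study.

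**Conclusion.** The concern holds. Sections 8.3.3 and 8.2.1 contradict each other; this is not simply missing detail, because applying the first as worded excludes events that the second expressly counts. For SAEs the conflict decides limb A, since its other two criteria are always met.

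The consequence is bounded. An under-count of total UADEs is possible but not established, because limb B may recover some events. The number affected is unknown and may be zero. The percentages above rest on the assumed denominator of randomized participants, and the per-arm figure also assumes tabulation by arm. The conclusion is drawn from the protocol text alone, without the Safety Management Plan or the assessment form. It should be fixed because UADE frequency is a stated safety measure and, with few events expected, a single classification would be visible in the table.

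**What to change.** Reconcile sections 8.3.3 and 8.2.1 before safety data are classified. Either route would work.

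1. Keep two ratings and state explicitly how an event with inconclusive evidence is treated under limb A's relatedness criterion.
2. Use in section 8.3.3 the levels that section 8.2.1 already names, with a definition for each. The intermediate wording in the unanticipated-problem definition could be adapted from research procedures to the device; the probable level would need a new definition.

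Whichever is chosen, use the same scale in the AE/SAE assessment form, the Safety Management Plan and the section 10.4.2 summary.

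The cost is protocol wording and, under the second route, a revised rating field. Section 14 requires an amendment with IRB approval before a permanent change is implemented. Participants provide no additional data. The drawback is that more events may be tabulated as device-related.

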8.4 Documenting and Reporting AE and SAEs

The designated study team will report an event to the Sponsor-Investigator within 24 hours of awareness. The investigator should make every attempt to obtain as much information as possible and must assess the relationship of the event to the study device and complete the AE/SAE assessment form. It is understood that more may be learned about the event after the initial report and this information may and should be updated as collected.

Any event that the sponsor determines is/are reportable to the IRB will be made within 5 working days of when the Sponsor-Investigator makes that determination. If it should be determined that an event presents an unreasonable risk to all participants, the study or parts of the study presenting that risk will be terminated as soon as possible.

8.5 Safety Monitoring

8.5.1 Safety Procedures At Screening

Study participants will be asked to self-report on recent suicidal thoughts including current suicidal ideation with plan and/or intent as well as attempts in the past 12 months. Responses are not monitored in real time. Participants who endorse having a current suicidal plan and/or intent or an attempt in the past 12 months will be excluded from the study. Participants will be notified that:

- They may benefit from a level of care beyond the scope of the study and investigational treatment.
- They should call 9-1-1 or go to their local emergency room and reach out to someone they trust and can help them stay safe if they feel they are in crisis or in need of medical attention.
- Will be electronically provided with a list of resources.

Participants who endorse current suicidal ideation with a plan and/or intent will also be notified that a member of the study team will attempt to follow-up with them. Three attempts will be made by the Study PI to contact participants with the third being by email and efforts/resolution will be documented in accordance with the study protocol. The study team will make every effort to follow-up with the participant within 3 business days of the initial report.

8.5.2 Unscheduled Visits

[figure not shown]
Study participants are welcome to initiate contact anytime throughout the duration of the study. If the contact is attributable to safety reasons or if the study team learns about a suspected safety event at any time, then an Unscheduled Visit would ensue, wherein the qualified study personnel would attempt to follow-up with the participant, and if it is determined that they are in immediate risk for hurting themselves or others, appropriate steps would be taken.

[figure not shown]
8.5.3 Week 2/EOS Safety Event Self-Report

[figure not shown]
Study participants will be asked to self-report on potential safety events at the Week 2 / EOS timepoint. Questions will explicitly ask about changes since starting the study (about 2 weeks ago) in their (1) mental and/or physical health, (2) any new thoughts about ending their life including new intent/plan/or attempts, and (3) any worsening of symptoms that led to changes in their medical care including medications taken for a psychiatric condition and/or therapy. Information gathered through this survey will be used to inform the need for follow-up, AE/SAE/UADE determination, and resolution.

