11. Ethics and Responsibilities	33
11.1 Good Clinical Practice	33
11.2 Institutional Review Board	33
11.3 Informed Consent	34
12. Records Management	35
12.1 Source Documentation	35
12.2 Case Report Form Completion and Data Management	35
12.3 Study Files and Record Retention	36
13. Auditing and Monitoring	36
13.1 Protocol Adherence and Deviations	37
14. Amendments	37
15. Study Start and Termination	38
16. Confidentiality	38
17. References	38

Schedule of Events

Visit Weeks/Days	Screening Period	Treatment Period	
	Screening / Baseline Day -6 to Day 1	Week 1 Day 3 (+2)	Week 2 (EOS/ET) Day 14 (+6)
Informed Consent	X		
Eligibility Confirmation (Inclusion/Exclusion)	X		
Demographics	X		
Psychiatric History	X		
Prior & Concomitant Medications/Therapy	X		X
[REDACTED]	[REDACTED]		
[REDACTED]	[REDACTED]		[REDACTED]
[REDACTED]	[REDACTED]		[REDACTED]
Participant Identity Verification ^a	X		
Randomization	X		
Register within the Study Application	X		
CSQ-8 ^b			X
[REDACTED]		[REDACTED]	[REDACTED]
[REDACTED]		[REDACTED]	[REDACTED]
[REDACTED]		[REDACTED]	[REDACTED]
[REDACTED]			[REDACTED]
Assessment of AE/SAEs			X
App Engagement Metrics (collected throughout study)			X
Termination of App Access			X

^a Video call with designated study team member ^b Self-Report Clinical Assessment
EOS = End of Study
CSQ-8 = Client Satisfaction Questionnaire; [REDACTED]

Participants will have up to one week from the time of providing informed consent to complete all screening and baseline tasks including registering for the study application. Participants will not be withdrawn for failing to register for the app. Date of randomization will be considered Day 1.

1. Introduction

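### The only AE question put to every participant dates the start of the study about two weeks back, while AE collection starts at consent, 13 to about 26 days before the survey

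*Combined protocol and SAP*

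**What the plan says.** Section 8.3.1 sets the collection window: "Collection of AEs and SAEs will begin at ICF signature, and will continue through End of Study (EOS) at Week 2".

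The Schedule of Events fixes its two ends. The first column is headed "Screening / Baseline Day -6 to Day 1", and the note below the table adds: "Participants will have up to one week from the time of providing informed consent to complete all screening and baseline tasks". The note also sets the origin of the day count: "Date of randomization will be considered Day 1". The final visit is headed "Week 2 (EOS/ET) Day 14 (+6" in days, so the survey may be completed from Day 14 to Day 20. Section 3.1 agrees in outline: one week of screening, two weeks of intervention and one week to complete the final survey, up to four weeks in all.

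The schedule row "Assessment of AE/SAEs" is marked once, in the Week 2 column. Several other rows are redacted, but this one is legible. Section 8.3 lists four sources of AEs, and the only one that asks participants directly is described as "Direct participant self reports collected via the Week 2 survey at EOS". The others are spontaneous reports, the Language Detection Protocol and review of selected transcripts.

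Section 8.5.3 describes what that survey asks: "changes since starting the study (about 2 weeks ago", covering mental and physical health, new suicidal thoughts, plans or attempts, and worsening that led to a change in care. The answers feed the AE/SAE/UADE determination.

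**The concern.** The survey question carries two time references: the start of the study, and a point about two weeks before the survey. They agree for someone who consents and is randomized on the same day and answers on Day 14. They separate as screening lengthens or the survey is completed later. The plan does not say what starting the study means for one participant. Section 15 defines a start date only for the study as a whole, as the first participant's consent. The only concrete cue a respondent gets is therefore the two-week gloss, and that is the part that fits the window in 8.3.1 least well.

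This matters because no other source asks everyone. Spontaneous reports are unprompted. Transcript review covers selected conversations. The Language Detection Protocol acts on free text typed in the app and, as 8.5.4 describes it, offers resources and does not ask about events. Participants stay in the study even if they never register for the app (Schedule of Events note; Section 4.3), so the in-app sources cannot reach all of them. If the gloss shortens recall, events soon after consent are less likely to be reported, and the effective recall period depends on when each person answers. Section 10.4.2 reports a plain n(%) for each safety endpoint, which would not show this.

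**Working it through.** No power or event formula applies. The check is day arithmetic on the visit windows.

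**Inputs**
- Consent: Day -6 at the earliest, Day 1 at the latest (Schedule of Events).
- Randomization: Day 1 (note to the schedule).
- EOS survey: Day 14 to Day 20 (Schedule of Events).
- AE window: consent to EOS (8.3.1).
- Gloss: about two weeks, taken here as exactly 14 days. This is an assumption, and it is the strictest reading.
- Day 0: the documents do not say whether there is one, so both counts are shown. Day -6 to Day 1 is 7 elapsed days with a Day 0 and 6 without. Only the first equals the full week allowed for baseline tasks.

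**The plan's own figure.** Section 3.1 gives up to four weeks: 7 + 14 + 7 = 28 days. Day -6 to Day 20 spans 27 calendar days with a Day 0 and 26 without. Both are within 2 days of 28, so the windows and the stated duration agree.

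**Shortfall of a literal 14-day look-back**

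Elapsed days = EOS day minus consent day, less 1 if consent is before Day 1 and there is no Day 0. Shortfall = max(0, elapsed days − 14).

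| Consent | EOS survey | Elapsed days | Shortfall |
|---|---|---|---|
| Day 1 | Day 14 | 14 − 1 = 13 | 0 |
| Day 1 | Day 20 | 20 − 1 = 19 | 5 |
| Day -6 | Day 14 | 14 + 6 = 20, or 19 | 6, or 5 |
| Day -6 | Day 20 | 20 + 6 = 26, or 25 | 12, or 11 |

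In the last row the shortfall is 12/26 = 46% or 11/25 = 44% of the elapsed time.

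**Period after randomization only.** Shortfall = max(0, EOS day − 1 − 14). This is zero up to Day 15 (15 − 1 − 14 = 0), 1 day at Day 16 and 5 days at Day 20. For a Day 20 respondent, 20 − 14 = Day 6, so the days before the look-back point are Days 1 to 5, when the assigned app is first available.

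**The case against.** The strongest reply is that the operative anchor is the start of the study and the parenthesis only approximates it. A participant who takes that start to be the day of consent covers the whole window, whatever the gloss says. A reader might infer that events before the last 14 days are excluded by design, or that the prompt covers only 14/26 = 54% of the window. The documents do not support either as a general statement. The 54% needs consent on Day -6, a survey on Day 20, and an approximate phrase read as exactly 14 days and allowed to override the main anchor.

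Other points also stand:
- Section 8.5.3 describes the questions and may not reproduce them, so the wording participants see may differ.
- Up to a week of the largest shortfall precedes randomization. Those events belong to collection under 8.3.1 but say little about the safety of the app.
- Participants may contact the team at any time (8.5.2), and the in-app sources operate once the app is used, so early events have other routes to detection.
- One prompt is described for both arms, and nothing in the documents shows a difference in capture between them.
- Safety is an exploratory aim (10.4.1) reported descriptively (10.4.2).

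These points limit the size of the problem. They do not reconcile 8.5.3 with 8.3.1, because the only explicit time cue still fits just those participants with a short screening period and a prompt survey.

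**Conclusion.** The mismatch is real and small. The only universal AE prompt is ambiguous about its recall period, and its concrete cue understates the consent-to-survey window by 0 to about 11 to 12 days. Counted from randomization, the understatement is zero for surveys completed by Day 15 and at most 5 days at Day 20. The likely effect is some under-reporting of screening-period events and, among late responders, of events in the first days of app use.

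The sizes rest on reading the gloss as 14 days and are upper limits on what wording alone could hide. The actual loss cannot be estimated: the documents give neither the number of late responders nor the distribution of time from consent to randomization. It would be wrong to conclude that early events are systematically excluded. This is a low-cost improvement to an exploratory safety endpoint. It does not bear on the primary satisfaction endpoint.

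**What to change.** Reconcile 8.5.3 with 8.3.1. Delete the two-week gloss and have the survey platform insert each participant's own consent date, for example: *since you joined the study on [date]*. Section 11.3 has the participant date the electronic consent form, so the date is already on record. Every respondent then has an anchor that matches the plan's collection window, whenever the survey is completed. If the live survey already uses such a date, only the description in 8.5.3 needs correcting.

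The cost is one text change and one piped date field, with no added burden on participants. Section 11.2 requires written IRB approval for protocol amendments and for written information given to participants, so routine approval of the revised wording should be allowed for.
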